Introduction: Glycemic control in acutely ill stroke patients with hyperglycemia is vital. Although insulin is the choice of anti-diabetic agent during acute stage, it is not clear which insulin regimen is better in terms of glycemic control and prevention of hypoglycemia in hospitalized acute stroke patients who are usually on small frequent nasogastric tube feeding. The present study aims to evaluate the efficacy and safety of human insulin (regular insulin and neutral protamine hagedorn, NPH insulin) to analog insulin (basal insulin glargine and rapid acting insulin aspart) in hospitalized acute stroke patients with hyperglycemia.

Justification: Analog insulins are developed by minor alteration of the amino acid chain which alters their pharmacokinetics and make them more physiological. However, these insulins are costly and are not widely available. Conventional human insulins are more commonly used in our country. Comparison of these two regimen is necessary in our own setting to optimize optimal glycemic management of hospitalized acute stroke patients.

Methodology: In this single-center, open-label, randomized trial, 100 patients with acute stroke and hyperglycemia (capillary blood glucose ≥ 10 mmol/L on 2 or more occasions) or history of type 2 DM admitted in the in-patient Department of Neurology, National Institute of Neurosciences (NINS) & Hospital will be randomly assigned to receive human insulin or modern insulin therapy in 1:1 ratio. The study will be carried out from February to June 2021. Blood glucose (BG) will be monitored by standardized glucometer thrice a day and insulin dose will be adjusted daily. The primary outcome of the study will be the differences in glycemic control between groups, as measured by mean daily BG concentration during the hospital stay. Secondary outcomes include differences between treatment groups in any of the following measures: number of hypoglycemic events (BG < 3.9 mmol/L), total daily dose of insulin, length of hospital stay, hospital complications and mortality.

Expected outcome/ result: The result will clearly show the efficacy and safety of newer insulins in comparison to conventional human insulin.

Recommendation: The study may help generating recommendations about insulin use in hospitalized acute stroke patients.

Section-C

INTRODUCTION:

It is well known that good clinical outcome in hospitalized patients with hyperglycemia cannot be expected unless target blood glucose is promptly achieved and maintained (1-3). This is also true for acute stroke patients. Hyperglycemia may affect the outcome of both ischemic and hemorrhagic stroke (4-6). Pro-oxidative and proinflammatory state imposed by hyperglycemia can cause direct neuronal toxicity. An increase of cerebral edema may be caused by hyperglycemia-mediated increase in matrix metalloproteinase-9 causing neuronal damage. Moreover, hyperglycemia may be responsible for a procoagulant state that can further compromise blood supply to the penumbral areas in acute ischemic stroke (7).

Management of hyperglycemia in acute stroke patients is particularly challenging because many of the patients cannot take their usual food and need feeding by nasogastric (NG) tube. Common practice is to feed 200 ml of liquid food (soup or milk) 2 hourly starting at morning and continue up to night (10 feeds/day). As such, insulin regimen used to control hyperglycemia in patients taking three major meals may not be appropriate in this setting. Moreover, many acute stroke patients receive corticosteroid therapy, which further deteriorates glycemic status. Dislodgement of NG tube may result in interruption of interruption of feeding, predisposing to hypoglycemia. All these challenges need to be kept in mind while choosing appropriate insulin regimen.

Hyperglycemia in hospitalized patients is defined as blood glucose levels >7.8 mmol/L. Insulin therapy should be initiated for treatment of persistent hyperglycemia starting at a threshold ≥ 10.0 mmol/L. Once insulin therapy is started, a target glucose range of 7.8–10.0 mmol/L is recommended for the majority of critically and non-critically ill patients (8). More stringent goals, such as <7.8 mmol/L may be appropriate for selected patients, as long as this can be achieved without significant hypoglycemia.

In most instances in the hospital setting, insulin is the preferred treatment for hyperglycemia (8). Human insulin in the form of regular insulin and intermediate acting insulin (neutral protamine hagedorn; NPH) are the most common insulin used for glycemic control in people with diabetes. However, they may not mimic the physiological insulin secretion pattern properly. As a result, tight glycemic control often leads to hypoglycemia. To improve the pharmacokinetics of the insulin, minor structural alterations are made to produce analogs insulin that have similar pharmacodynamics properties. These include long acting basal insulin like insulin detemir, glargine and degludec and rapid acting prandial insulin like insulin lispro, aspart or glulisine. These modern insulins are costlier and availability is often limited.

An insulin regimen with basal, prandial, and correction components is the preferred treatment for non-critically ill hospitalized patients with good nutritional intake (9). Clinical guidelines from

professional organizations recommend the use of subcutaneous insulin in the form of basal-bolus regimen as the preferred therapy for glycemic control in hospitalized medical and surgical patients with type 2 diabetes mellitus (T2DM) (8,10,11). Sliding scale regular human insulin regimen or premixed insulin in acute setting is strongly discouraged by current recommendations (12). These recommendations are mainly based on studies done on patients taking three major meals.

Use of regular insulin thrice a day is a common practice in our setting mainly due to its simplicity and relevance to feeding practice in acute stroke patients. Nevertheless, this regimen is associated with limited therapeutic success because of the lack of basal insulin coverage. Adding a long acting basal insulin in the form of NPH or basal insulin analogs are often not introduced in-hospital settings due to fear of hypoglycemia (9). Modern basal insulin analogs may be superior in this respect as they have more physiological pharmacokinetic properties (13).

In different countries, basal-bolus therapies with insulin analogs are being used more commonly. But intermediate-acting and regular human insulin are also observed to have almost similar efficacy and safety (12,14). No inpatient trials have been conducted in our region to determine optimal treatment regimens for hospitalized patients with T2DM in special situation like acute stroke. As there are significant differences in patient demographics, admission cause, feeding practice and availability of hospital resources between patients of developed and developing countries, the choice of agents may not be similar (15,16). In this background, the present study aims to compare the efficacy and safety of conventional human insulin (regular insulin and intermediate acting NPH insulin) to newer analog insulin (basal insulin glargine with rapid acting insulin aspart) in acute stroke patients with hyperglycemia admitted in a referral tertiary neuroscience institute of Dhaka.

RATIONALE:

One in five patients hospitalized for acute stroke has hyperglycemia. For optimum outcome of these patients, proper glycemic control is essential. Acute stroke patients, who need hospitalization, are usually unable to take food normally and they are fed through nasogastric tube with small frequent feeding (200 ml, 2-hourly, 10 feed/day). It is not clear which insulin regimen will suit better to these type of feeding practice. Moreover, corticosteroids (dexamethasone) are often used in these patients as treatment adjunct which further challenges glucose homeostasis. Different insulin regimens are used in such patients but none is validated in clinical trials. Episodes of hypoglycemia may cause further neurological deterioration in acute stroke patients. So regimen with less chance of hypoglycemia needs to be identified. Although analog insulins are observed to have less chance of hypoglycemia, they are costly and had not been well studied in our setting. It is essential for us to know the efficacy and safety of analog insulin regimen in comparison to human insulin, so that appropriate management decision can be made

OBJECTIVES:

General objective:

- To compare the efficacy and safety of human insulin (regular insulin and intermediate acting NPH insulin) to analog insulin (basal insulin glargine and rapid acting insulin aspart) in hospitalized acute stroke patients with hyperglycemia

Specific objectives:

In hospitalized acute stroke patients with hyperglycemia -

- To evaluate the efficacy and safety of human insulin (regular insulin and intermediate acting NPH insulin)
- To assess the efficacy and safety of insulin analog (basal insulin glargine and rapid acting insulin aspart)
- To compare the efficacy and safety of two insulin regimen
- To evaluate the socio-demographic and clinical characteristics of the patients included in two treatment arms

METHODOLOGY:

Type of study: Single-center, open-label, randomized trial

Place of Study: Department of Neurology, National Institute of Neurosciences & Hospital, Dhaka.

Study Period: February to June, 2021

Study population: Patients admitted in the Department of Neurology with acute stroke and hyperglycemia

Sample Size:

Sample size was calculated according to following formula for non-inferiority trial (17):

$$N = 2 \times \left(\frac{Z_{1-\alpha} + Z_{1-\beta}}{\delta_0} \right)^2 \times S^2$$

Here, N= sample size per group

$$\alpha = 0.05$$

$$\beta = 0.20$$

δ_0 = a clinically acceptable margin (assumed as 3 mmol/L of blood glucose)

S² = Pooled standard deviation of both comparison group = 8

So,

$$N_{\text{non-inferiority}} = 2 \times \left(\frac{1.645 + 0.845}{3} \right)^2 \times 6^2 = 50$$

As a result, 50 patients will be randomly assigned to two treatment groups (50 human insulin regimen, 50 analog insulin regimen).

Inclusion criteria

- Patients admitted to adult neurology ward with acute stroke with
- Patients having hyperglycemia (capillary blood glucose ≥ 10 mmol/L in 2 or more occasions or having history of treatment for DM)
- Patients with age of 18-80 years of both sexes
- Patients or their attendants giving consent to take part in the study

Exclusion Criteria

- Patients with hyperglycemic emergencies (hyperglycemic hyperosmolar state or diabetic ketoacidosis)
- Pregnant patients
- Those not giving consent to participate in the study

Study Procedure

Patients will be randomly assigned to receive either a human insulin regimen (starting with regular insulin three times a day with NPH insulin twice a day) or analog insulin regimen (basal insulin glargine once daily and insulin aspart three times a day) following a computer-generated randomization table. All oral antidiabetic drugs will be discontinued on admission.

For a patient who is known to have diabetes but were not getting insulin previously (or previous insulin dosage is not known), insulin therapy will be started at a total daily dose of 0.3-0.4 units/kg/day for an admission BG between 10-15 mmol/L or 0.5-0.6 units/kg/day for a BG >15 mmol/L. In previously insulin treated patients, ongoing total daily dose of insulin will be started. If there is history of poor glycemic control with ongoing insulin dose, then 10-20% increase of daily dose of insulin will be considered.

For a patient who is not known to have diabetes, insulin therapy will be started if admission BG is >10 mmol/L in two or more occasions. A total daily dose of 0.3-0.4 units/kg/day will be started if admission BG is 10-15 mmol/L and 0.5-0.6 units/kg/day for a BG >15 mmol/L.

Patients treated with human insulin regimen will receive 50% of total daily dose as NPH insulin at around 6 am and 6 pm, while the rest 50% regular human insulin three times a day in 3 equally divided doses at around 6 am, 12 pm and 6 pm.

Patients treated with modern insulin regimen will receive 50% of total daily dose as basal insulin glargine at the same time of day and 50% as insulin aspart given in 3 equally divided doses at 6 am, 12 pm and 6 pm.

In both groups, insulin dosage will be adjusted daily to a target fasting and premeal BG 7.8-10.0 mmol/L in the absence of hypoglycemia. Insulin dosage will be adjusted daily according to BG values. If the fasting and/or premeal BG is 10-15 mmol/L in the absence of hypoglycemia, the total daily dose will be increased by 10% every day. If the fasting and/or premeal BG is >15 mmol/L, the insulin daily dose will be increased by 20% every day. If a patient develops hypoglycemia (BG <3.9 mmol/L), the insulin daily dose will be decreased by 20%. Supplemental regular insulin will be given in addition to scheduled mealtime insulin for BG >10 mmol/L using a supplemental insulin protocol.

BG will be measured before each bolus insulin injection (at 6 am, 12 pm and 6 pm). Glycated hemoglobin (HbA1c) will be measured after hospital admission if not done within last three months.

Except anti-diabetic treatment, other treatments will be continued as per the decisions of the treating physicians. If NG feeding is discontinued and patient is kept NPO, conventional group will receive neutralizing insulin with any dextrose containing fluid along with low dose NPH insulin, if needed. Modern insulin group will receive neutralizing insulin with any dextrose containing fluid with glargine insulin as before.

After recruitment, each recruited patient will be visited daily (even in holidays according to a predefined schedule) by one of the investigators and insulin dose will be adjusted according to glucose profile of previous day. Insulin injection and capillary blood glucose monitoring by glucometer will be done by trained nurses as part of their routine patient care. Doctors and nurses on duty will be provided with cell number of the investigators who will receive call on 24/7 basis for any emergency or uncertainty regarding management of hyperglycemia.

Hypoglycemia is regarded as the only short-term adverse event of insulin. As both treatment arms will use established and recognized insulin regimen, no compensation will be provided to the patient or his/her attendants in case of any adverse event. As most of the hospitalized patients have severe stroke with case fatality rate around 20%, death will not be regarded as parameter of primary treatment outcome.

During discharge, last in-hospital insulin dose will be continued with education to the caregiver regarding insulin injection and glucose monitoring technique. No follow up visit is included in the study.

Protocol deviation and protocol violation:

Deviation to protocol will be recorded and reported to ethical committee as soon as possible. Failure to obtain informed written consent, use of incorrect insulin regimen, not fulfilling inclusion and exclusion criteria will be regarded as protocol violation and will be reported to ethical committee immediately. In case of protocol violation, the data of related participant will be discarded.

Outcome variables

The primary efficacy outcome of the study will be the differences in glycemetic control between groups, as measured by mean daily BG concentration during the hospital stay.

The primary safety outcome will be the frequency of hypoglycemic events (BG <3.9 mmol/L).

Secondary outcomes include differences between treatment groups in any of the following measures: total daily dose of insulin, length of hospital stay, hospital complications, and mortality.

Data collection technique

Data will be collected in a predesigned questionnaire by the research team. The researchers will recheck randomly and blindly to verify the collected data.

Data management

All data will be compiled and edited meticulously by thorough checking and rechecking. All omissions and inconsistencies will be corrected and will be removed methodically.

Statistical analysis

Computer based statistical analysis will be carried out with appropriate techniques and systems by SPSS 22.0. Quantitative data will be expressed as mean and standard deviation or median and inter-quartile range; and qualitative data will be expressed as frequency and percentage. Continuous variables, analysis will be made by the Students T-test or Mann-Whitney *U* test. Categorical variables will be analyzed by the χ^2 test. All probabilities will be 2-tailed. Statistical significance will be accepted at $p \leq 0.05$.

Utilization of results

The result of study will be helpful for the physicians to choose appropriate insulin regimen in patients hospitalized with acute stroke having hyperglycemia. It will also help the policy makers in ensuring adequate supply of appropriate insulin that may help improve the outcome of patients.

FLOW CHART

Sl. No.	Job Title	Feb'21	Mar'21	Apr'21	May'21	Jun'21
1.	Questionnaire Validation	√				
2.	Data Collection	√	√	√		
3.	Data Analysis				√	
4.	Report writing and Printing				√	√
5.	Submission					√

ETHICAL IMPLICATIONS:

Prior to the commencement of this study, approval of the institutional review board (IRB) of National Institute of Neurosciences & Hospital, Dhaka will be sought. The aims and objectives of the study along with its procedure, risks and benefits of this study will be explained to the patients or attendants of the patients in easily understandable local language and then written consent will be taken from each. It will be assured that all information and records would be kept confidential.

Role of funding agency

The funding agency will have no role in protocol development, data collection, analysis, interpretation or writing the report. The authors will have full access to all study data and will have the final responsibility for the decision to submit for publication.

REFERENCES:

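### The sample-size section states a pooled SD of 8, labels it S², and then calculates with 6²; the stated value does not give 50 per group.

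*Combined protocol and SAP*

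**What the plan says.** The Sample Size paragraph uses a non-inferiority formula for two means, N = 2 × ((Z(1−α) + Z(1−β)) / δ₀)² × S², where "N= sample size per group". It sets α = 0.05, β = 0.20 and a margin δ₀ of 3 mmol/L. It then defines S² as "Pooled standard deviation of both comparison group = 8". The worked line that follows puts in 1.645, 0.845, 3 and 6², and gives 50. The allocation is accordingly "50 human insulin regimen, 50 analog insulin regimen".

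The total appears again in the summary's Methodology paragraph and in the Abstract for IRB/Ethical Committee, both of which speak of "100 patients with acute stroke and hyperglycemia". Neither repeats the calculation or mentions an SD. Under Outcome variables, the primary efficacy outcome is glycemic control "as measured by mean daily BG concentration during the hospital stay", so the SD needed is the between-patient SD of that quantity.

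**The concern.** Two adjacent lines give different values for the input that fixes the sample size. There is also a labelling fault: S² is the symbol for a variance, but it is described as a standard deviation. The 8 can therefore be read as an SD of 8 or as a variance of 8 (SD 2.83), and the worked line uses neither.

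The 100-patient total and the 80% power are justified nowhere else in the protocol. If the SD really is 8, the trial is well short of its stated power. If 8 is the variance, it is far larger than its stated margin requires. If 6 was meant, the numbers stand and only the text is wrong. A reader or ethics committee cannot tell which of these applies.

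**Working it through.** **Inputs**, all from the Sample Size paragraph: Z values 1.645 and 0.845; margin 3 mmol/L; S² = 8 as stated, or 6² = 36 as used; 50 per group.

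**Step 1: reproduce the plan's figure.** The multiplier is 2 × ((1.645 + 0.845)/3)² = 2 × 0.83² = 1.3778. With S² = 36, N = 1.3778 × 36 = 49.6, hence 50 per group. The worked line is correct for SD 6. Solving backwards from 50 gives SD = 3 × √(50/2) / 2.49 = 6.02.

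**Step 2: put in the stated 8.**
- As an SD: 1.3778 × 64 = 88.2.
- As a variance: 1.3778 × 8 = 11.0.

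The exact normal quantile for 80% power is 0.8416 rather than 0.845. With exact quantiles the three results are 49.46, 87.93 and 10.99, so the choice moves N by at most one patient per group (50; 88 or 89; 11 or 12). Power of 85% or 90%, one-sided α of 0.025, and 50 taken as a total were also tried. None of these makes 8 yield 50.

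**Step 3: what 50 per group delivers.** Power = Φ(3 / (SD × √(2/50)) − 1.645), where √(2/50) = 0.2, assuming no true difference and a one-sided 0.05 test. The margin that 50 per group supports at 80% power is 2.486 × SD × 0.2.

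| Reading | SD × 0.2 | 3 / (SD × 0.2) | Power (normal) | Power (t, 98 df) | N per group for 80% | Margin at 80% power, n = 50 |
|---|---|---|---|---|---|---|
| SD 6 | 1.2 | 2.500 | Φ(0.855) = 80.4% | 79.9% | 50 | 2.98 mmol/L |
| SD 8 | 1.6 | 1.875 | Φ(0.230) = 59.1% | 58.6% | 88–89 | 3.98 mmol/L |
| Variance 8 (SD 2.83) | 0.566 | 5.303 | Φ(3.658) > 99.9% | > 99.9% | 11–12 | 1.41 mmol/L |

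Under SD 8, the chance of failing to show non-inferiority when the regimens are truly equal is 1 − 0.591 = 41%.

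**Step 4: is changing the digit enough?** No. If the definition line were changed to S² = 6 and nothing else, a literal reading would give 1.3778 × 6 = 8.3 per group. The label has to be corrected as well.

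**The case against.** The best defence is that this is one wrong digit. The worked line, the 50/50 allocation and the total of 100 all agree with SD 6, and two of the three readings leave power at about 80% or higher. SD 8 also looks implausible beside the protocol's own glucose figures. For illustration, assume a mean of 10 mmol/L (the top of the 7.8–10.0 target range) and a normal distribution. SD 8 would then put about 22% of patients' average glucose below the 3.9 mmol/L hypoglycemia threshold and about 11% below zero. A digit misread in converting the PDF is also possible.

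Part of this stands. A slip for 6 is a reasonable guess, the worked line shows exactly how 50 was obtained, and a loss of power is not established. But the allocation and the total follow from the 6² line, so they are not independent evidence that 6 was intended. The plausibility argument does not single out SD 6 either: under the same assumptions SD 6 puts about 16% below 3.9 and 5% below zero, whereas for SD 2.83 the mean minus two SDs is still about 4.3 mmol/L. Skewness or a higher mean would change all of these, so they do not settle the matter. A misread digit would not explain why S² is called a standard deviation or why no source is given.

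A second point limits the figures rather than the finding. They all assume the one-sided 0.05 non-inferiority test in the formula, whereas the Statistical analysis section says "All probabilities will be 2-tailed" and describes no non-inferiority test. At one-sided 0.025, SD 6 would need 63 per group and SD 8 would need 112. The protocol also discards the data of patients with protocol violations, so 50 analysed per group is not assured. Those are separate issues.

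**Conclusion.** The concern holds. The stated variability of 8 does not reproduce 50 per group under either reading; only the 6 in the worked line does, and the protocol does not say which value was intended. The power of the planned trial is about 80%, 59% or above 99.9% depending on the reading, given a 3 mmol/L margin, one-sided 0.05, no true difference and 50 analysed per group. It is not shown that the trial is underpowered. What is shown is that the input fixing the sample size contradicts itself, so the sample-size justification must be corrected before it can support the stated N and power.

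**What to change.** In the Sample Size paragraph, give one value for the SD of patient-level mean daily blood glucose, in mmol/L and with its source. Call it S if it is an SD or S² if it is a variance, and make the definition and the worked line agree. Then:

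- **If SD 6 is meant:** correct the definition line, both value and label. N and power stand under the formula as written.
- **If SD 8 is meant:** correct the worked line and state that 50 per group gives about 59% power for the 3 mmol/L margin.
- **If variance 8 is meant:** correct the worked line and report the power (above 99.9%) or the margin (about 1.4 mmol/L at 80% power) that 50 per group supports.

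Each of these is a text change with no extra patients. Enrolment would rise only if SD 8 is meant and the sponsor chose to keep 80% power at 3 mmol/L, to 88–89 per group (176–178 in total).

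### The sample-size SD (listed as 8, used as 6) has no source and no link to the per-patient mean glucose, so the stated 80% power is unsupported

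*Combined protocol and SAP*

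**What the plan says.** All places are in the combined protocol and SAP, Section-C, Methodology.

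- **Sample Size.** The formula is for a non-inferiority comparison of two means, with alpha 0.05, beta 0.20 and "a clinically acceptable margin (assumed as 3 mmol/L of blood glucose"). The spread is entered under the symbol S² as "Pooled standard deviation of both comparison group = 8". The next line substitutes 6 squared and obtains 50, hence "50 human insulin regimen, 50 analog insulin regimen". The cited reference is given for the formula. No source or unit is given for the SD.
- **Outcome variables.** The primary efficacy outcome is glycemic control "as measured by mean daily BG concentration during the hospital stay".
- **Study Procedure.** "BG will be measured before each bolus insulin injection (at 6 am, 12 pm and 6 pm"), so each patient's average rests on three readings a day. In both arms "insulin dosage will be adjusted daily to a target fasting and premeal BG 7.8-10.0 mmol/L". The daily dose is raised by 10% at 10-15 mmol/L and by 20% above 15. At the lower end: "If a patient develops hypoglycemia (BG <3.9 mmol/L), the insulin daily dose will be decreased by 20" percent.
- **Statistical analysis.** Continuous variables are compared by t-test or Mann-Whitney test. All tests are two-tailed at 0.05.

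**The concern.** The formula needs the between-patient SD of the quantity that will be compared. A t-test or Mann-Whitney test needs independent observations, so that quantity is most naturally one average per patient over the stay. The documents give no SD for it. Averaging several readings per patient removes part of the reading-to-reading variation, and titrating both arms to one target should narrow the spread further. An SD of 6 or 8 mmol/L looks large beside a target range only 2.2 mmol/L wide (10.0 - 7.8).

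This goes beyond choosing between 6 and 8: settling on either would still leave a figure that nobody has tied to the outcome. At stake is the power claim. Required size grows with the square of the SD, so the claim that 50 per group gives 80% power is only as good as this one number.

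**Working it through.** **1. Reproduce the plan's figure.** Inputs from Sample Size: z values 1.645 and 0.845, margin 3, SD 6, true difference 0.

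n = 2 × (2.490/3)² × 6² = 49.6, so 50 per group. It reproduces.

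**2. Use the listed value instead.**
- 8 as an SD: 2 × (2.490/3)² × 64 = 88.2, about 88 per group.
- 8 as a variance, as the symbol S² says (SD = √8 = 2.83): 2 × (2.490/3)² × 8 = 11.0, about 11 per group.

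Of these readings, only SD 6 gives 50.

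**3. Does 6 or 8 fit a whole-stay patient average?** The documents state no expected mean or shape, so both are assumed here. The gamma and lognormal are matched to the same mean and SD.

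| Assumed mean | SD | Shape | Below 3.9 | Above 15 | Above 20 |
|---|---|---|---|---|---|
| 10 | 6 | normal | 15% (5% below zero) | 20% | 5% |
| 10 | 6 | gamma | 13% | 18% | 7% |
| 10 | 6 | lognormal | 8% | 16% | 6% |
| 10 | 8 | normal | 22% (11% below zero) | 27% | 11% |
| 12 | 6 | normal, gamma, lognormal | 9%, 4%, 2% | 31%, 27%, 24% | 9%, 10%, 9% |
| 15 | 6 | normal, gamma, lognormal | 3%, 0.5%, <0.1% | 50%, 45%, 42% | 20%, 19%, 17% |

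Example, first row: Φ((3.9 - 10)/6) = Φ(-1.017) = 15%.

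Raising the mean empties the lower tail but fills the upper one. At mean 15, 42-50% of patients would average above 15 over the whole stay, despite a rule that raises the dose by 20% a day above that level.

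**4. Power at 50 per group, margin 3, true difference 0.** The standard error is SD × √(2/50) = 0.2 × SD. Power = Φ(3/(0.2 × SD) - z), with z = 1.645 for one-sided 0.05 or 1.96 for one-sided 0.025, which matches two-tailed 0.05.

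| SD | 3/(0.2 × SD) | Power, one-sided 0.05 | Power, one-sided 0.025 |
|---|---|---|---|
| 2.83 | 5.30 | >99.9% | >99.9% |
| 4 | 3.75 | 98% | 96% |
| 4.5 | 3.33 | 95% | 92% |
| 6 | 2.50 | 80% | 71% |
| 8 | 1.875 | 59% | 47% |

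**5. Difference that 50 per group can exclude with 80% power.** At one-sided 0.05: 2.490 × 0.2 × SD ≈ 0.5 × SD, which is 1.4 mmol/L at SD 2.83, 2.0 at SD 4 and 3.0 at SD 6. At one-sided 0.025: (1.96 + 0.842) × 0.2 × SD ≈ 0.56 × SD.

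**The case against.** A reader might infer that 6 or 8 cannot be the SD of the patient averages. The documents do not support that. They give no expected mean, length of stay or within-patient correlation. Patients who qualify on glucose enter at 10 mmol/L or more, dexamethasone is described as often used, and the target is approached in daily steps of 10-20%. A wide spread of averages is therefore possible, and at mean 12 a skewed shape leaves only 2-4% below 3.9. This stands: the SD is implausible under stated assumptions, not ruled out.

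A reader might also infer that true power is nearly 100%. That rests on treating 6 as the SD of single readings. The SD of an average of k readings with correlation ρ is S × √(ρ + (1 - ρ)/k). With k = 21 and ρ = 0.2-0.5 (assumed; neither is in the documents), S = 6 gives SD 2.9-4.3 and power from 96.5% to above 99.9%. But the listed S = 8 with ρ = 0.5 gives SD 5.8 and 83%, close to the plan's figure. No single replacement power can be defended.

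Finally, one might argue that a smaller SD would let a regimen that is truly 1.5 mmol/L worse pass too easily. Such a regimen lies inside the margin that the plan itself calls acceptable, so that is a complaint about the margin, not the SD.

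One value per patient is also an inference. It is the natural reading, but the plan does not state it.

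**Conclusion.** The point holds in this form: the SD is contradictory (8 under a variance symbol, 6 in the arithmetic), has no unit or source, and is not tied to the primary outcome. Either value is implausibly large for whole-stay patient averages under daily titration, though not impossible. The 80% is correct only for SD 6 with one-sided alpha 0.05. Across the readings of the plan's own numbers, power at 50 per group runs from 59% to above 99.9% at one-sided 0.05, and from 47% to above 99.9% at the planned two-tailed level.

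The direction is unknown. Below SD 6 the trial has more power for the 3 mmol/L margin than stated; above it, less. It should not be read as shown to be too small or too large.

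These figures assume one value per patient, 50 analysable patients per group, a true difference of zero and the normal approximation. The tail percentages also assume the means and shapes shown.

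**What to change.** - State one SD for the per-patient mean daily glucose, in mmol/L and with its source (for example ward charts). Write S and S² separately, and reconcile 6 with 8.
- State that the primary comparison uses one value per patient.
- Keep 50 per group. Restate power for the 3 mmol/L margin over a range of SDs, at the alpha and sidedness of the planned analysis. Give the difference that 50 per group can exclude with 80% power (about 0.5 × S at one-sided 0.05, 0.56 × S at one-sided 0.025).

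This costs protocol wording and one recalculation, with no extra patients. The downside is that 50 per group may no longer follow from the 3 mmol/L margin. If the sourced SD is smaller than 6, the justification should rest on the smaller difference that 50 per group can exclude. If it exceeds about 6.0 (3/0.498), or about 5.4 (3/0.560) at the two-tailed level, the plan should say plainly that power for the margin is below 80%.
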